## **7.7. Intercurrent medical conditions that may lead to elimination of a subject from Per-Protocol analyses**

For vaccinated subjects, at each study visit subsequent to the vaccination visit, it must be verified if the subject has experienced or is experiencing any intercurrent medical condition. If it is the case, the condition(s) must be recorded in the eCRF.

For the infectivity controls group, at each study visit subsequent to the sporozoite challenge visit, it must be verified if the subject has experienced or is experiencing any intercurrent medical condition. If it is the case, the condition(s) must be recorded in the eCRF.

Subjects may be eliminated from the Per-Protocol set (PPS) for analysis of immunogenicity and efficacy if, during the study, they incur a condition that has the capability of altering their immune response or are confirmed to have an alteration of their initial immune status.

## **8. HEALTH ECONOMICS**

Not applicable.

## 9. SAFETY

The investigator or site staff is/are responsible for the detection, documentation and reporting of events meeting the criteria and definition of an AE or SAE as provided in this protocol.

Each subject will be instructed to contact the investigator immediately should they/the subject manifest any signs or symptoms they perceive as serious.

### 9.1. Safety definitions

#### 9.1.1. Definition of an adverse event

An AE is any untoward medical occurrence in a clinical investigation subject, temporally associated with the use of a medicinal product, whether or not considered related to the medicinal product.

An AE can therefore be any unfavorable and unintended sign (including an abnormal laboratory finding), symptom, or disease (new or exacerbated) temporally associated with the use of a medicinal product. For marketed medicinal products, this also includes failure to produce expected benefits (i.e., lack of efficacy), abuse or misuse.

Examples of an AE include:

- Significant or unexpected worsening or exacerbation of the condition/indication under study.
- Exacerbation of a chronic or intermittent pre-existing condition including either an increase in frequency and/or intensity of the condition.
- New conditions detected or diagnosed after study vaccine administration even though they may have been present prior to the start of the study.
- Signs, symptoms, or the clinical sequelae of a suspected interaction.
- Signs, symptoms, or the clinical sequelae of a suspected overdose of either study vaccine or a concurrent medication (overdose per se should not be reported as an AE/SAE).
- Signs, symptoms temporally associated with study vaccine administration.
- Pre- or post-treatment events that occur as a result of protocol-mandated procedures (i.e., invasive procedures, modification of subject's previous therapeutic regimen).

AEs to be recorded as endpoints (solicited AEs) are described in Section 9.1.3. All other AEs will be recorded as UNSOLICITED AEs.

Examples of an AE DO NOT include:

- Medical or surgical procedures (e.g., endoscopy, appendectomy); the condition that leads to the procedure is an AE/SAE.
- Situations where an untoward medical occurrence did not occur (e.g., social and/or convenience admission to a hospital, admission for routine examination).
- Anticipated day-to-day fluctuations of pre-existing disease(s) or condition(s) present or detected at the start of the study that do not worsen.
- Pre-existing conditions or signs and/or symptoms present in a subject prior to the study vaccination. These events will be recorded in the medical history section of the eCRF.

### **9.1.2. Definition of a serious adverse event**

A SAE is any untoward medical occurrence that:

- a. Results in death,
- b. Is life-threatening,

Note: The term 'life-threatening' in the definition of 'serious' refers to an event in which the subject was at risk of death at the time of the event. It does not refer to an event, which hypothetically might have caused death, had it been more severe.

- c. Requires hospitalization or prolongation of existing hospitalization,

Note: In general, hospitalization signifies that the subject has been admitted at the hospital or emergency ward for observation and/or treatment that would not have been appropriate in the physician's office or in an out-patient setting. Complications that occur during hospitalization are also considered AEs. If a complication prolongs hospitalization or fulfills any other serious criteria, the event will also be considered serious. When in doubt as to whether 'hospitalization' occurred or was necessary, the AE should be considered serious.

Hospitalization for elective treatment of a pre-existing condition (known or diagnosed prior to informed consent signature) that did not worsen from baseline is NOT considered an AE.

- d. Results in disability/incapacity, OR

Note: The term disability means a substantial disruption of a person's ability to conduct normal life functions. This definition is not intended to include experiences of relatively minor medical significance such as uncomplicated headache, nausea, vomiting, diarrhea, influenza like illness, and accidental trauma (e.g., sprained ankle) which may interfere or prevent everyday life functions but do not constitute a substantial disruption.

- e. Is a congenital anomaly/birth defect in the offspring of a study subject.

Medical or scientific judgement should be exercised in deciding whether reporting is appropriate in other situations, such as important medical events that may not be immediately life-threatening or result in death or hospitalization but may jeopardize the subject or may require medical or surgical intervention to prevent one of the other outcomes listed in the above definition. These should also be considered serious. Examples of such events are invasive or malignant cancers, intensive treatment in an emergency room or at home for allergic bronchospasm, blood dyscrasias or convulsions that do not result in hospitalization.

### **9.1.3.     Solicited adverse events**

#### **9.1.3.1.     Solicited local (injection-site) adverse events**

The following local (injection-site) AEs will be solicited:

**Table 17     Solicited local adverse events**

Pain at injection site
Redness at injection site
Swelling at injection site

#### **9.1.3.2.     Solicited general adverse events**

The following general AEs will be solicited:

**Table 18     Solicited general adverse events**

Fatigue
Fever
Gastrointestinal symptoms*
Headache

\*Gastrointestinal symptoms include nausea, vomiting, diarrhea and/or abdominal pain.

Note: It is recommended that subjects measure and record the oral body temperature in the evening. Should temperature (including additional) measurements be performed at other times of day, subjects will be instructed to record the highest temperature in the diary card.

### **9.1.4.     Clinical laboratory parameters and other abnormal assessments qualifying as adverse events or serious adverse events**

In absence of diagnosis, abnormal laboratory findings (e.g., clinical chemistry, hematology, urinalysis) or other abnormal assessments that are judged by the investigator to be clinically significant will be recorded as AE or SAE if they meet the definition of an AE or SAE (refer to Sections 9.1.1 and 9.1.2). Clinically significant abnormal laboratory findings or other abnormal assessments that are present at baseline and significantly worsen following the start of the study will also be reported as AEs or SAEs.

The investigator will exercise his or her medical and scientific judgement in deciding whether an abnormal laboratory finding or other abnormal assessment is clinically significant.

## 9.1.5. Adverse events of specific interest

### 9.1.5.1. Potential immune-mediated diseases

Potential immune-mediated diseases (pIMDs) are a subset of AEs that include autoimmune diseases and other inflammatory and/or neurologic disorders of interest which may or may not have an autoimmune aetiology. AEs that need to be recorded and reported as pIMDs include those listed in [Table 19](#).

However, the investigator will exercise his/her medical and scientific judgement in deciding whether other diseases have an autoimmune origin (i.e., pathophysiology involving systemic or organ-specific pathogenic autoantibodies) and should also be recorded as a pIMD.

**Table 19 List of potential immune-mediated diseases**

Neuro-inflammatory disorders	Musculoskeletal disorders	Skin disorders

 
• Cranial nerve neuropathy, including paralysis and paresis (e.g., Bell's palsy).
 
• Optic neuritis.
 
• Multiple sclerosis.
 
• Transverse myelitis.
 
• Guillain-Barré syndrome, including Miller Fisher syndrome and other variants.
 
• Acute disseminated encephalomyelitis, including site specific variants, e.g., non-infectious encephalitis, encephalomyelitis, myelitis, myeloradiculoneuritis.
 
• Myasthenia gravis, including Lambert-Eaton myasthenic syndrome.
 
• Demyelinating peripheral neuropathies including: 
 
- Chronic inflammatory demyelinating polyneuropathy,
 
- Multifocal motor neuropathy,
 
- Polyneuropathies associated with monoclonal gammopathy.
 
 
 
• Narcolepsy.
 
	
 
• Systemic lupus erythematosus and associated conditions.
 
• Systemic scleroderma (systemic sclerosis), including: 
 
- Diffuse scleroderma,
 
- CREST syndrome.
 
 
 
• Idiopathic inflammatory myopathies, including: 
 
- Dermatomyositis,
 
- Polymyositis.
 
 
 
• Anti-synthetase syndrome.
 
• Rheumatoid arthritis and associated conditions including: 
 
- Juvenile idiopathic arthritis,
 
- Still's disease.
 
 
 
• Polymyalgia rheumatica.
 
• Spondyloarthropathies, including: 
 
- Ankylosing spondylitis,
 
- Reactive arthritis (Reiter's syndrome),
 
- Undifferentiated spondyloarthritis,
 
- Psoriatic arthritis,
 
- Enteropathic arthritis.
 
 
 
• Relapsing polychondritis.
 
• Mixed Connective Tissue disorder.
 
• Gout.
 
	
 
• Psoriasis.
 
• Vitiligo.
 
• Erythema nodosum.
 
• Autoimmune bullous skin diseases (including pemphigus, pemphigoid and dermatitis herpetiformis).
 
• Lichen planus.
 
• Sweet's syndrome.
 
• Localized scleroderma (Morphea).
 

Vasculitis	Blood disorders	Others

 
Large vessels vasculitis including: 
 
Giant Cell Arteritis (Temporal Arteritis),
 
Takayasu's Arteritis.
 
 
 
Medium sized and/or small vessels vasculitis including: 
 
Polyarteritis nodosa,
 
Kawasaki's disease,
 
Microscopic Polyangiitis,
 
Wegener's Granulomatosis (granulomatosis with polyangiitis),
 
Churg-Strauss syndrome (allergic granulomatous angiitis or eosinophilic granulomatosis with polyangiitis),
 
Buerger's disease (thromboangiitis obliterans),
 
Necrotizing vasculitis (cutaneous or systemic),
 
Anti-neutrophil cytoplasmic antibody (ANCA) positive vasculitis (type unspecified),
 
Henoch-Schonlein purpura (IgA vasculitis),
 
Behcet's syndrome,
 
Leukocytoclastic vasculitis.
 
 
 
	
 
Autoimmune hemolytic anemia.
 
Autoimmune thrombocytopenia.
 
Antiphospholipid syndrome.
 
Pernicious anemia.
 
Autoimmune aplastic anemia.
 
Autoimmune neutropenia.
 
Autoimmune pancytopenia.
 
	
 
Autoimmune glomerulonephritis including: 
 
IgA nephropathy,
 
Glomerulonephritis rapidly progressive,
 
Membranous glomerulonephritis,
 
Membranoproliferative glomerulonephritis,
 
Mesangioproliferative glomerulonephritis,
 
Tubulointerstitial nephritis and uveitis syndrome.
 
 
 
Ocular autoimmune diseases including: 
 
Autoimmune uveitis,
 
Autoimmune retinitis.
 
 
 
Autoimmune myocarditis.
 
Sarcoidosis.
 
Stevens-Johnson syndrome.
 
Sjögren's syndrome.
 
Alopecia areata.
 
Idiopathic pulmonary fibrosis.
 
Goodpasture syndrome.
 
Raynaud's phenomenon.
 

Liver disorders	Gastrointestinal disorders	Endocrine disorders

 
Autoimmune hepatitis.
 
Primary biliary cirrhosis.
 
Primary sclerosing cholangitis.
 
Autoimmune cholangitis.
 
	
 
Inflammatory Bowel disease, including: 
 
Crohn's disease,
 
Ulcerative colitis,
 
Microscopic colitis,
 
Ulcerative proctitis.
 
 
 
Celiac disease.
 
Autoimmune pancreatitis.
 
	
 
Autoimmune thyroiditis (Hashimoto thyroiditis).
 
Grave's or Basedow's disease.
 
Diabetes mellitus type I.
 
Addison's disease.
 
Polyglandular autoimmune syndrome.
 
Autoimmune hypophysitis.
 

When there is enough evidence to make any of the above diagnoses, the AE must be reported as a pIMD. Symptoms, signs or conditions which might (or might not) represent the above diagnoses, should be recorded and reported as AEs but not as pIMDs until the final or definitive diagnosis has been determined, and alternative diagnoses have been eliminated or shown to be less likely.

In order to facilitate the documentation of pIMDs in the eCRF, a pIMD standard questionnaire and a list of preferred terms (PTs) and PT codes corresponding to the above diagnoses will be available to investigators at study start.

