## 9.2. Events or outcomes not qualifying as adverse events or serious adverse events

### 9.2.1. Pregnancy

Female subjects who become pregnant after the vaccination will not receive the sporozoite challenge may continue the study for safety follow-up only, at the discretion of the investigator.

While pregnancy itself is not considered an AE or SAE, any adverse pregnancy outcome or complication or elective termination of a pregnancy for medical reasons will be recorded and reported as an AE or a SAE.

Note: The pregnancy itself should always be recorded on an electronic pregnancy report.

The following should always be considered as SAE and will be reported as described in Sections 9.4.1 and 9.4.3:

- Spontaneous pregnancy loss, including:
  - Spontaneous abortion, (spontaneous pregnancy loss before/at 22 weeks of gestation),
  - Ectopic and molar pregnancy,
  - Stillbirth (intrauterine death of fetus after 22 weeks of gestation).
- Any early neonatal death (i.e., death of a live born infant occurring within the first 7 days of life).
- Any congenital anomaly or birth defect (as per [CDC MACDP] guidelines) identified in the offspring of a study subject (either during pregnancy, at birth or later) regardless of whether the fetus is delivered dead or alive. This includes anomalies identified by prenatal ultrasound, amniocentesis or examination of the products of conception after elective or spontaneous abortion.

Furthermore, any SAE occurring as a result of a post-study pregnancy AND considered by the investigator to be reasonably related to the study vaccine will be reported to GSK Biologicals as described in Section 9.4.3. While the investigator is not obligated to actively seek this information from former study participants, he/she may learn of a pregnancy through spontaneous reporting.

**9.3. Detecting and recording adverse events, serious adverse events and pregnancies****9.3.1. Time period for detecting and recording adverse events, serious adverse events and pregnancies**

*Only for the P-Fx and NP-Fx groups:*

All AEs starting within 21 days following administration of the dose of study vaccine (Day 1 to Day 21) must be recorded into the appropriate section of the eCRF, irrespective of intensity or whether or not they are considered vaccination-related.

SAEs that are related to the study vaccine will be collected and recorded from the time of the receipt of study vaccine until the subject is discharged from the study.

*For all subjects:*

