The time period for collecting and recording AEs post-challenge will begin at the first day of challenge (Day 22) up to 29 days post-challenge (Day 50).

The time period for collecting and recording AEs of specific interest (pIMDs and meningitis) will begin at Day 1 (for P-Fx and NP-Fx groups)/the first day of sporozoite challenge (Day 22) (for infectivity control group) and will end at the last study visit (Day 190 for the P-Fx and NP-Fx groups/Day 50 for the infectivity control group). See Section 9.4 for instructions on reporting of pIMDs.

The time period for collecting and recording SAEs will begin at Day 1 (for P-Fx and NP-Fx groups)/the first day of sporozoite challenge (Day 22) (for infectivity control group) and will end at the last study visit (Day 190 for the P-Fx and NP-Fx groups/Day 50 for the infectivity control group) for each subject. See Section 9.4 for instructions on reporting of SAEs.

All AEs/SAEs leading to withdrawal from the study will be collected and recorded from Day 1 (for P-Fx and NP-Fx groups)/the first day of sporozoite challenge (Day 22) (for infectivity control group).

In addition to the above-mentioned reporting requirements and in order to fulfil international reporting obligations, SAEs that are related to study participation (i.e., protocol-mandated procedures, invasive tests, a change from existing therapy) or are related to a concurrent GSK medication/vaccine will be collected and recorded from the time the subject consents to participate in the study (screening) until she/he is discharged from the study.

The time period for collecting and recording pregnancies will begin at Day 1 (for P-Fx and NP-Fx groups)/the first day of sporozoite challenge (Day 22) (for infectivity control group) and will end at the last study visit (Day 190 for the P-Fx and NP-Fx groups/Day 50 for the infectivity control group). See Section 9.4 for instructions on reporting of pregnancies.

An overview of the protocol-required reporting periods for AEs, SAEs and pregnancies is given in [Table 20](#).

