### 9.3.2. Post-study adverse events and serious adverse events

A post-study AE/SAE is defined as any event that occurs outside of the AE/SAE reporting period defined in [Table 20](#). Investigators are not obligated to actively seek AEs or SAEs in former study participants. However, if the investigator learns of any SAE at any time after a subject has been discharged from the study, and he/she considers the event reasonably related to the study vaccine, the investigator will promptly notify the Study Contact for Reporting SAEs.

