### **9.5. Follow-up of adverse events, serious adverse events and pregnancies**

#### **9.5.1. Follow-up of adverse events and serious adverse events**

##### **9.5.1.1. Follow-up during the study**

After the initial AE/SAE report, the investigator is required to proactively follow each subject and provide additional relevant information on the subject's condition to GSK Biologicals (within 24 hours for SAEs; refer to [Table 23](#)).

All SAEs and AE of specific interest (pIMDs and meningitis) (serious or non-serious) documented at a previous visit/contact and designated as not recovered/not resolved or recovering/resolving will be reviewed at subsequent visits/contacts until the last visit of the subject.

All AEs documented at a previous visit/contact and designated as not recovered/not resolved or recovering/resolving will be reviewed at subsequent visits/contacts until 30 days after vaccination/challenge, as applicable.

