#### **9.5.1.2. Follow-up after the subject is discharged from the study**

The investigator will follow subjects:

- With SAEs, AE of specific interest (pIMDs or meningitis) (serious or non-serious), or subjects withdrawn from the study as a result of an AE, until the event has resolved, subsided, stabilized, disappeared, or until the event is otherwise explained, or the subject is lost to follow-up.

If the investigator receives additional relevant information on a previously reported SAE, he/she will provide this information to GSK Biologicals using a paper/electronic Expedited Adverse Events Report and/or pregnancy report as applicable.

GSK Biologicals may request that the investigator performs or arranges the conduct of additional clinical examinations/tests and/or evaluations to elucidate as fully as possible the nature and/or causality of the AE or SAE. The investigator is obliged to assist. If a subject dies during participation in the study or during a recognized follow-up period, GSK Biologicals will be provided with any available post-mortem findings, including histopathology.

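### A non-serious suspected pIMD that starts on Days 51-190 in a vaccinee, prompts no withdrawal and is undiagnosed by Day 190 falls outside the AE and pIMD recording rules

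*Protocol*

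**What the plan says.** **Where a suspected pIMD goes.** Protocol section 9.1.5.1 (text after Table 19) requires a pIMD report once there is enough evidence for a listed diagnosis. Until then, possible cases "should be recorded and reported as AEs but not as pIMDs until the final or definitive diagnosis has been determined".

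**When the AE record is open.** Section 9.3.1 sets two windows. For the vaccinated groups, "All AEs starting within 21 days following administration of the dose of study vaccine (Day 1 to Day 21) must be recorded". For all subjects, post-challenge AE recording "will begin at the first day of challenge (Day 22) up to 29 days post-challenge (Day 50"). Table 4 marks no AE recording at Visit 23 (Day 190).

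**When the pIMD record is open.** Also in section 9.3.1: "The time period for collecting and recording AEs of specific interest (pIMDs and meningitis) will begin at Day 1" for vaccinees and at challenge for controls, and it "will end at the last study visit (Day 190 for the P-Fx and NP-Fx groups/Day 50 for the infectivity control group"). Table 4 marks pIMD and meningitis recording at Visit 23. The secondary endpoint (section 11.2) and the planned tables (Protocol section 11.11, SAP section 5.5.1) use the same Day 190 limit for vaccinees.

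**Follow-up.** Under section 9.5.1.1, SAEs and AEs of specific interest are reviewed to the last visit, but other unresolved AEs "will be reviewed at subsequent visits/contacts until 30 days after vaccination/challenge, as applicable". After discharge, section 9.5.1.2 covers subjects "With SAEs, AE of specific interest (pIMDs or meningitis) (serious or non-serious), or subjects withdrawn from the study as a result of an AE". Section 9.4.5 triggers the expedited pIMD report on diagnosis.

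**The concern.** The pIMD rule sends an unconfirmed case to the AE record, and the time-window rule closes that record 140 days before pIMD recording ends. From Day 51 a site that follows both rules has nowhere to enter signs that might be a pIMD, unless they are serious or cause withdrawal. The diagnosis may come only after Day 190. In that case there is no safety record from which the event could later be reclassified, and no rule keeps the subject under follow-up.

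Section 1.3.1 names pIMD as an important potential risk of the vaccine and says that cases will be described. The occurrence of pIMDs to Day 190 is a secondary safety endpoint. A possible case of a named risk should leave a trace in the safety data even when work-up is incomplete at the last visit.

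**Working it through.** **Inputs**
- AE windows: Days 1-21 after vaccination and Days 22-50 after challenge (Protocol 9.3.1).
- pIMD window: Days 1-190 for vaccinees; challenge (Day 22) to Day 50 for controls (Protocol 9.3.1 and 11.11; SAP 5.5.1).
- Visit 22 to Visit 23: 140 days, allowed 126-154 (Protocol Table 6, SAP Table 1).
- Review limit for ordinary AEs: 30 days after challenge (Protocol 9.5.1.1).
- About 40 vaccinees (Protocol 5.1).

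**1. Reproduce the plan's figure.** Visit 23 minus Visit 22 = 190 − 50 = 140 days, as in Table 6.

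**2. Length of the gap.** AE recording covers 21 + 29 = 50 days. The vaccinee pIMD window has 190 days. Days with pIMD recording but no ordinary AE recording: 190 − 50 = 140, and 140/190 = 74%. For controls both windows end at Day 50, so the gap is 0 days.

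**3. Cases that start by Day 50.** These are recorded as AEs. Required review ends at Day 22 + 30 = Day 52. The next scheduled visit after Day 50 is Day 190, so Visit 22 is in practice the last scheduled review. That leaves 190 − 52 = 138 days of the pIMD window without required review. Section 9.5.1.2 does not cover the case after discharge, because it is not yet an AE of specific interest.

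**4. Routes open to a suspected pIMD with onset on Days 51-190 in a vaccinee**

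| Situation | Recorded as | Planned safety table? |
|---|---|---|
| Serious | SAE, to Day 190 (9.3.1) | Yes |
| Leads to withdrawal | AE leading to withdrawal (9.3.1) | Yes, to Day 190 |
| Diagnosed by Day 190 | pIMD (9.1.5.1, 9.4.5) | Yes |
| None of these | Intercurrent medical condition (7.7; Table 4, Visit 23) | No |

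Section 7.7 collects intercurrent conditions to decide per-protocol eligibility. Neither Protocol 11.11 nor SAP 5.5.1 tabulates them, and no follow-up attaches to them. The last row is the gap.

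**5. Can the loss be sized?** Only under assumptions that are not in the documents. Let onset be uniform over Days 1-190, let the delay from first sign to diagnosis be a fixed d days, and let every case be non-serious without withdrawal. A case is lost if its onset is on Days 51-190 and onset + d exceeds 190, so the share is d/190 for d up to 140:
- d = 30: 30/190 = 16%
- d = 60: 60/190 = 32%
- d = 90: 90/190 = 47%
- d of 140 or more: 140/190 = 74%

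These are ceilings for the chosen delays, since serious cases and withdrawals would be captured.

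**6. What one case changes.** With 40 vaccinees and Clopper-Pearson limits, 1/40 is 2.5% (95% CI 0.1 to 13.2) and 0/40 is 0% (0 to 8.8).

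**The case against.** The strongest reply is that much still gets through, and most of that reply stands.

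- **Other rules run past Day 50.** A reader might infer that a late suspected case is captured by no rule at all. The table above shows otherwise. SAEs include important medical events by investigator judgement (section 9.1.2), and several conditions in Table 19 would plausibly qualify. Intercurrent conditions are documented in the eCRF at Visit 23. This narrows the gap to non-serious cases without withdrawal, but an intercurrent-condition entry is not a safety record.
- **The diagnostic bar is not absolute.** The sentence in section 9.1.5.1 goes on to accept that alternatives are merely less likely, and section 9.1.5.1 leaves room for judgement on unlisted diseases. A full work-up is therefore not always needed before a pIMD is entered. This shortens the delay but does not reopen the AE record.
- **A compatible reading exists.** Section 9.1.5.1 gives no end date, so a site could keep entering suspected cases as AEs to Day 190. But Table 4 provides no AE recording at Visit 23 and the planned general AE tables stop at Day 50. Sites would have to guess, and such an entry would still not be tabulated.
- **Post-study status.** A reader might infer that section 9.3.2 makes these events post-study, since it covers "any event that occurs outside of the AE/SAE reporting period defined in" Table 20. The period bars of Table 20 are not legible in the copy reviewed, and SAE and pIMD reporting runs to Day 190. I do not rely on that reading.
- **Endpoint.** The pIMD table counts diagnosed cases, so opening the AE screen alone would not change the percentage. This is correct. The count can change only through follow-up that later confirms a case.

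**Conclusion.** The rules conflict, within a narrow scope. In P-Fx and NP-Fx, a suspected pIMD with onset on Days 51-190 that is non-serious, leads to no withdrawal and is undiagnosed by Day 190 has no place in the AE or pIMD record and no required follow-up. One that starts by Day 50 is recorded but drops out of required review at about Day 52. Controls have no recording gap.

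The gap is 140 of 190 days on the nominal schedule (126-154 days between the two visits under the allowed intervals). A reader might take the 74% as the share of pIMDs lost. The documents do not support that: it is a share of days, and it would be a share of cases only if every diagnosis took at least 140 days and no case was serious or led to withdrawal. The share lost cannot be estimated from the documents. Any effect on the pIMD count can only be downward, and all analyses are descriptive (Protocol 11.12, SAP 6). The conclusion rests on reading the section 9.3.1 windows as limits on AE recording, as Table 4 does. Efficacy is not affected. This is a worthwhile, inexpensive correction.

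**What to change.** Reconcile Protocol sections 9.1.5.1, 9.3.1, 9.5.1.1 and 9.5.1.2 and Table 4:

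- Record on the AE screen any sign, symptom or condition that the investigator considers a possible pIMD, with onset from Day 1 to Day 190 in vaccinees, under a 'suspected pIMD' flag. Keep that entry open at Visit 23.
- Follow flagged events under section 9.5.1.2 until confirmed or ruled out, including those that began by Day 50.
- In Protocol section 11.11 and SAP section 5.5.1, count cases confirmed later in the pIMD table by onset date, and list unresolved suspected cases separately.

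The cost is protocol and SAP wording, one eCRF flag at a visit that already records pIMDs, and follow-up of the few flagged subjects. No visit is added, and the efficacy analysis is unchanged.
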